### PROCESS AND OUTPUT INDICATORS

Input measures included all resources and activities provided per city. Process and output measures monitored achievements within each arm of the intervention and included the following:

1. Percentages of pharmacies, pharmacy workers, and physicians/midwives completing training and continuing in follow up.
2. Monthly reports of STD cases seen at pharmacies and by private physicians and midwives in the intervention cities.
3. Evaluation by standardized simulated patients to follow changes in patterns of symptom recognition, counseling, and referral by pharmacy workers in intervention and control cities at baseline, 3, 6, and 18 months post training.
4. Sentinel surveillance of STD cases seen at pharmacies from control and intervention cities at 3, 9, and 18 months post-initiation of the intervention.
5. Number of FSW screened by the mobile team in each cycle.
6. FSW prevalence of CT by cycle and number of previous screenings by the MT.
7. FSW prevalence of GC by cycle and number of previous screenings by the MT.
8. FSW prevalence of TV by cycle and number of previous screenings by the MT.

---

Q Revision to add additional potential secondary outcomes: HSV2, HTLV, or Hepatitis B virus seropositivity; and HPV and *M. genitalium* (UW IRB Approval 1/31/2005)

9. Percent of FSW with positive CT, GC or TV adequately treated by the MT.
10. Percent of FSW reporting condom use with last client.
11. Quantity of selected drugs purchased by and dispensed in pharmacies, number of condoms distributed and sold.

## SURVEY POPULATION

Cross-sectional surveys in two populations were implemented in order to determine the impact of the community intervention in the general population of young adults and in FSW. Secondary groups included FSW clients recruited at commercial sex venues (200 from each city) in 2002-03.R

### **General Population Survey (GPS)**

The baseline 2002 GPS included men and women ages 18 to 29 years, residents of the 24 cities selected as candidates for the PREVEN study trial. The number of participants in baseline surveys for each of the 24 cities included 300 men and 300 women (250 random sample plus the first 50 partners identified as living in the households of these participants). In outcome surveys in 2005 and 2006 in the 20 cities participating in the intervention trial, the numbers of participants for each of the 20 cities included 300 men and 300 women, totaling 12,000. Recruitment timeframe totaled three months.

### Inclusion Criteria

- Men and women ages 18 to 29 years at enrollment.
- Residence for a minimum of 6 months in the city where interview takes place.
- Lived in the city for at least 3 of the last 6 months.
- Spends at least 4 nights a week in the household where identified.

---

R Client surveys were discontinued after the baseline 2002-03 survey after found to not differ substantially from men in the general population.

- Mentally capable of providing informed consent and of responding to a questionnaire.
- Willing to participate in the survey by providing independent verbal informed consent.

#### Exclusion Criteria

- Inability to provide informed consent.

#### Participant Retention and Withdrawal

- No follow-up of participants required, and therefore no measures for retention were planned. Participants able to voluntarily withdraw from the study for any reason at any time.

#### **FSW Survey**

For this study, FSW were defined as women who offer their personal sex services at venues of sex work identified in the participating cities. The goal for each survey included 200 FSW enrolled in each of the cities (24 cities at baseline and 20 cities in outcome surveys), for a total of 4,800 at baseline and 4,000 in 2005 and in 2006. Enrollment was carried out in the same cities selected for the GPS conducted during 2002-03 for the baseline survey and 2005 and 2006 surveys, and according to the same timeline and timeframe as the GPS in the 2005 and 2006 surveys (3 months).

#### Inclusion Criteria

- Women found offering sex services at selected venues during pre-scheduled visits.
- Age 18 years or older.S
- Mentally capable of providing informed consent and responding to a questionnaire.
- Willing to participate in the survey by providing independent verbal informed consent.

---

S Revision to include sex workers ages 14 years and older (UW IRB approval 12/17/2004)

*Participation in previous surveys, including our own previous STD surveys, does not preclude participation.*

#### Exclusion Criteria

- Inability to provide informed consent because of obvious mental impairment due to the use of alcohol or drugs, or to other mental illness.

#### Participant Retention and Withdrawal

- No follow-up of participants is required, and therefore no measures for retention are planned. Participants may voluntarily withdraw from the study for any reason at any time.

### SAMPLING AND SURVEY METHODS

#### **General Population Survey (GPS)**

The sampling frame for the study was based on data from the 1999-2000 pre-census household database compiled by the Peruvian National Institute of Statistics and Informatics (INEI). For our survey, INEI defines sampling sets with an average size of 80 households. These sets were divided into two equally sized clusters of approximately 40 households, so as to provide approximately 10 eligible participants per cluster. For each city, 108 clusters were selected using the random number generator of MS-Excel.

Field workers visited all households in the selected clusters, locating households with eligible members. A random sample of ten households with eligible members was selected from each cluster (or all households if less than ten). The interviewers returned to the selected households. If more than one household member met the inclusion criteria, the person with the most recent birthday was selected for participation. At this time, an appointment to meet the selected person was made. Selected participants then were interviewed to confirm eligibility

and to conduct the consent process to determine willingness to participate, and to complete the study procedures. Only in cases when eligibility of the participant could not be confirmed, the eligible person with the next most recent birthday was selected.

Field work was divided into nine periods lasting ten days each, corresponding to the nine independent samples selected for each city. Each interviewer covered four clusters during the first eight days of each period. Although the ninth day of the period was programmed for visits to participants not found during the initial visit, there was no set limit for the number of appointments made to find selected participants. Recruitment of participants continued until, at the end of a period, the gender-specific sample size has been reached or exceeded. We expected less than 100 clusters needed to reach the women's sample size, while in most cities, all 108 clusters must be visited to complete the sample size for men. Interviewers conducted field procedures wearing study gowns and carrying a backpack with survey materials and a small portable cooler containing frozen acrylamide gel bags.

A nine-day training course for field personnel included modules on: good clinical practice (GCP), ethics, basics of STDs, map handling, selection of participants, informed consent procedures, interviewing, sample collection and handling, and coding. The modules included formal lectures as well as demonstrations and hands-on laboratory practice. All course participants received a copy of an Interviewer's Manual for the study. For each city, a team of approximately three interviewers and a supervisor was selected. Trainees selected as supervisors also received a Supervisor's Manual. Health professionals, such as nurses, midwives, and medical doctors, comprised the interviewers and supervisors. Additionally, a team of six previously experienced regional coordinators and a national supervisor received training in this course. The course prepared all field personnel, supervisors, and coordinators, to be capable of conducting interviews.

## **FSW Survey**

Local teams began field activities by performing a census of sex work venues (places where FSW meet their potential clients, e.g. brothels, bars or streets). The health promoter and key informants within each city identified these venues. Team members recorded the location and characteristics of the venues, as well as the approximate number of FSW expected to be found at the venue at different times during an average week. The census ended when all accessible sex work venues were recorded. Although it was expected that not all sex work venues would be identified by the census, extremely hard-to-reach venues were considered to be likely of relatively low epidemiological importance, as they tended to serve small closed circles of clients. At the end of the census, copies of the field work records were sent to the UPCH in Lima. In cities with more than 200 FSW identified by the census, a sample of about 200 women were selected by the time-location sampling method. In cities where fewer than 200 FSW were identified, the local team attempted to enroll all FSW identified.

Local teams visited commercial sex venues and invited all FSW present in that venue to participate in the study, and completed interviews and sample collection for this study in a single visit for all participants. After providing verbal informed consent, study participants completed an interviewer-administered questionnaire and underwent HIV and STD counseling and testing. All participants received a copy of the informed consent. Basic demographic data were collected from any FSW present at the venue during the visit but who do not meet the eligibility criteria or who refuse to participate.

Field work teams for each city included three counselors, a laboratory technician and a health promoter, usually a peer FSW. All counselors attended a centralized training workshop before the beginning of field activities. In addition to training in selection of study participants and the appropriate completion of the study questionnaire, the workshop included modules on

ethical issues including appropriate consent procedures granting confidentiality and avoiding any form of coercion. Laboratory technicians received training on appropriate techniques for sample collection, processing, and shipping, as well as on biosafety.

## DATA COLLECTION

### **General Population Survey**

#### **Interview**

Participants responded to a face-to-face questionnaire administered by the interviewer. The questionnaire addressed data on demographic and household characteristics, travel, migration, labor, health seeking behavior, marriage, contraception, knowledge about STDs and reproductive health. Afterwards, the participants responded to a self-administered questionnaire, exploring characteristics of the participant's sexual behavior.T A GPS Interviewers Manual of Procedures (MOP) provided detailed instructions to guide and standardize all study procedures across sites; it was changed in 2005 and 2006 to include the collection of data with PDAs.

#### **Biological Sample Collection**

After questionnaire completion, the interviewers explained procedures for sample collection, asking men to provide first void urine (about 15 ml) for STD tests in a 50-ml plastic container. In 2002, females received a rack with 1 polyester/plastic stick vaginal swab and two cotton/wooden stick vaginal swabs, to be self-applied in that order by the participant. The interviewer placed the polyester swab in an empty 2 ml cryovial. The first cotton swab was used to inoculate an InPouchTV® culture for *T. vaginalis* in the field; and the second cotton swab to prepare a vaginal smear on a glass slide in the

---

T The questionnaire for the 2002 survey involves a paper format. The general population survey questionnaire

field. Females unwilling to provide self-applied vaginal swabs were asked to provide urine samples.U

After collection of salivaV and urine or vaginal samples, the interviewers collected venous blood samples from men and women using a vacuum extraction system, using syringes when extraction of blood with the vacuum system was difficult.

Participants providing biological samples received a booklet with information about HIV and the HIV tests as pre-test counseling for HIV and a referral card to be used at a local health center to receive STD/HIV counseling and to receive test results.

Urine samples, dry polyester swabs in cryovials, and blood samples were placed in a cooler for transportation to the local laboratory facilities for specimen processing and transport. *T. vaginalis* cultures and glass smears were transported to the laboratory inside the backpack.

Consent forms, referral cards, and samples were labeled using preprinted self-adhesive labels with alphanumeric codes and barcodes. The same code was entered into the hand-held computer.

## **FSW Survey**

### **Interview**

FSW responded to a face-to-face demographic and sexual history questionnaire, after providing anonymous, verbal informed consent for study participation and for the storage of blood for future testing. The FSW Interviewers Manual of Procedures (MOP)

---

changed from paper to PDA format prior to the second survey (UW IRB Approval 8/08/2005).

U During the 2006 survey, an extra polyester swab was collected prior to the other 3 swabs. This swab was placed by the interviewer in APTIMA® transport media and was used for the Gen-Probe APTIMA TMA for *N. gonorrhoeae*, *C. trachomatis*, and *T. vaginalis*.

provided detailed instructions to guide and standardize all study procedures across sites. When eligibility was not confirmed during the interview, the enrollment process was aborted promptly.

### **Biological Sample Collection**

Blood and vaginal swabs were collected from consenting participants following the same procedures described for the GPS, though in 2002, a clinician obtained an endocervical swab and vaginal swabs via speculum exam.W Participants received a referral card to be used at the local health center to obtain their laboratory test results, and received treatment if necessary. They also received condoms.

### **LABORATORY METHODS**

The urine sample, a dry polyester swab in a cryovial, and the blood sample were placed inside a cooler for transportation to the local laboratory. A cotton swab was used to inoculate *T. vaginalis* culture medium (InPouchTV, Biomed, Oregon, USA). A second cotton swab was used to prepare a glass slide for Gram stains. *T. vaginalis* culture specimens were transported at room temperature and placed in an incubator upon arrival to the local laboratory, where they were examined for motile *T. vaginalis* forms daily for 5 days. Glass slides were transported to the local laboratory to be stored for up to 7 days. Serum and urine aliquots, as well as prepared glass slides, were shipped weekly to the central laboratory in Lima. All specimens for NAAT were stored at -20°C and shipped frozen to the central laboratory for testing. Upon arrival to the central laboratory, the dry polyester swab was eluted in 2 ml of 2SP and stored at -20°C until processed.

---

V Saliva testing for HIV discontinued prior to second survey (UW IRB Approval 8/08/2005)

W For the 2005 and 2006 surveys of FSW, clinician swab collection discontinued and changed to self-obtained vaginal swabs only (UW IRB Approval 8/08/2005)

## **Gonococcal Infection**

REVISIONX: Specimens from 2002-2003 and 2005 surveys reported as gonorrhea positive in the AMPLICOR assay, according to manufacturer's instructions, were further tested by the Gen-Probe APTIMA assay, utilizing specimens suspended in 2SP, allowing final classification as positive or negative based upon the APTIMA assay. Specimens from the 2006 survey were tested first by the APTIMA assay and then all positive specimens were tested by the AMPLICOR assay. Positive results are confirmed by APTIMA testing of specimens suspended in 2SP. Gonococcal infection is defined by positive AMPLICOR plus positive APTIMA assays.

## **Chlamydial Infection**

REVISIONY: Specimens from the 2002-2003 and 2005 surveys reported as indeterminate by Roche AMPLICOR were tested by the Gen-Probe APTIMA Combo 2 Assay (Gen-Probe, San Diego, CA). The 2006 survey employed initial testing by the Gen-Probe Aptima assay utilizing the specimen collected in APTIMA transport medium; all positive specimens then were tested by the AMPLICOR assay performed on the specimen eluted in 2SP.

Results from the 2002-03 and 2005 surveys are considered positive if initially AMPLICOR positive; or if initially indeterminate and subsequently positive in the APTIMA assay. Specimens from the 2006 survey positive by both assays are considered positive. Those specimens yielding discordant results undergo APTIMA re-testing of specimens suspended in 2SP, for final classification as positive or negative. For these specimens, chlamydial infection is

---

X Rationale for revision: Target sequences in the methyltransferase gene of *N. gonorrhoeae* used in the AMPLICOR assay have been shown to be present in other *Neisseria* species and "false-priming" has been suggested with lactobacilli in this assay. In interim analysis, prior to unblinding of the data, we found that while 70% and 48% of urine and clinician-collected samples were APTIMA positive, respectively, only 12% of self-collected vaginal swab AMPLICOR positive specimens were positive for gonorrhea in the APTIMA assay. Those specimens AMPLICOR positive and APTIMA negative were much more likely to have had lower AMPLICOR optical density readings than were specimens positive in both tests (data not shown). This finding is consistent with previous reports associating apparent false-positive AMPLICOR results with lower test signal strengths.

Y Although studies have shown quite similar sensitivity and specificity of the Roche AMPLICOR and Gen-Probe APTIMA assays for chlamydial infection, the AMPLICOR assay yields an important proportion of specimens

defined by positive results in the APTIMA assay performed on the 2SP-suspended specimen. (See Appendix A: Laboratory Flow Charts).

### **Trichomonas vaginalis**

REVISIONZ: The Gen-Probe TV-TMA assay was used to test all 2002-03 and 2006 vaginal swab samples and to validate positive and a subset of negative InPouch culture results from the 2005 surveys. The final results showed high positive predictive values of InPouch positive cultures, in terms of APTIMA TV-TMA confirmation, in 17 of 20 cities, but no correlation of InPouch with TV-TMA in three cities; and showed low sensitivity of the InPouch cultures (approximately 50%) in relation to TV-TMA results in all cities.

### **Syphilis seroreactive**

The quantitative RPR test was utilized; specimens reported as RPR reactive were confirmed by the TP•PA test. As a surrogate for possible early syphilis, syphilis seroreactivity is defined by an RPR reactive  $\geq 1:8$  with a reactive TP•PA.

### **HIV**

Serum samples were tested by HIV ELISA; dually ELISA positive specimens were confirmed by Western blot. Aliquots of specimens reported as Western blot indeterminate in Lima are shipped to the University of Washington Retrovirology Laboratory for confirmatory Western blot testing.

### **Bacterial Vaginosis**

Gram stain smears were utilized for assessment of bacterial vaginosis. Bacterial vaginosis is defined by a Nugent score of  $\geq 7$ .

---

reported as “indeterminate” (equivocal or inhibited)

Z Rationale for protocol change: The 2006 DSMB review described unusually high prevalences of trichomoniasis in some of the 20 study cities.

### III. Statistical considerations

Descriptive methods (e.g. means, prevalences) and plots (e.g. STI prevalences over time) form the bases of initial analyses. We summarized participation rates, sample sizes, demographics (e.g., age, gender, marital status, education, etc.) and curable STI prevalences (*Chlamydia trachomatis*, *N. gonorrhoeae*, syphilis seropositivity, or vaginal trichomoniasis, HIV) overall, by city and by intervention arm for each survey (2002-03, 2005, 2006; FSW and GP). We also summarized condom use rates in the GP overall, by gender, by arm and among the following subgroups—men with commercial sex partners in the last year, men with male sex partners in the last year. For the baseline survey, we added testing of samples of sera for HSV-2 and HTLV seropositivity.

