**Definitions**

*Trichomonas vaginalis* positive – Initially positive in the Aptima TV-TMA assays performed on the specimen collected in the Gen-Probe collection media and subsequently positive in the Aptima TV-TMA assay performed on the 2SP-suspended specimen.

*Trichomonas vaginalis* negative – Initially negative in the Aptima TV-TMA assay or negative in the Aptima assay subsequently performed on the 2SP-suspended specimen.

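### The 2005 trichomonas prevalence rests on culture with about 50% sensitivity and is not comparable with the 2002-03 and 2006 NAAT values in the same descriptive time series

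*Supplement*

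**What the plan says.** Section III (Statistical considerations) of the 2010 Protocol Summary states that descriptive methods and "plots (e.g. STI prevalences over time) form the bases of initial analyses". Curable STI prevalences, with vaginal trichomoniasis listed among them, are summarised overall and "by city and by intervention arm for each survey (2002-03, 2005, 2006; FSW and GP"). No caveat about assays is attached.

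The Laboratory Methods section on *Trichomonas vaginalis* gives the assays. "The Gen-Probe TV-TMA assay was used to test all 2002-03 and 2006 vaginal swab samples". For 2005 the same assay served only "to validate positive and a subset of negative InPouch culture results from the 2005 surveys". The comparison showed "low sensitivity of the InPouch cultures (approximately 50%) in relation to TV-TMA results in all cities", and no correlation between culture and TMA in three of the 20 cities. The introduction and the footnote to the primary endpoint likewise confine the switch to NAAT to the baseline and 2006 specimens.

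The latest Data Analysis Plan differs on the baseline: its variables table still lists InPouch culture at baseline and Aptima in 2006 for **Tvresul**.

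**The concern.** A series over three surveys can be read as a trend only if each point measures the same thing. Here the middle point, the only one between baseline and outcome, uses a test that finds about half of what the outer two find. No section corrects, omits or flags it. A reader of the tables or plots could take a low 2005 value for a real decline and the 2006 value for a resurgence. In the three cities where culture did not track TMA, the 2005 city value says little about trichomonas. Three cities cannot divide evenly between two arms, so the 2005 arm summaries may also be affected unequally.

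**Working it through.** **The plan's own figure.** The sensitivity of about 50% cannot be reproduced, because no cross-tabulation of culture against TMA is given. It is used as stated, with 0.4 to 0.6 as an assumed range.

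**Inputs**
- General-population women at baseline (April 2006 trial summary, section 1.1): chlamydia 6.8%, gonorrhoea 0.8%, trichomonas 5.2%. Men: chlamydia 4.0%, gonorrhoea 0.3%.
- Syphilis in the general population: 1% (Table 2 planning value).
- Female sex workers (FSW; section 1.2): chlamydia 14.5%, gonorrhoea 3.5%, trichomonas 7.9%, RPR reactive 3.9%. The share at a titre of 1:8 or more is not given, so 0 to 3.9% is used.
- Equal numbers of men and women, as the survey plans.
- Assumptions: true prevalence constant, infections independent, no false-positive cultures.

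The summary does not name the assay behind 5.2% and 7.9%. Culture is the likelier reading, since that summary predates the NAAT re-testing. Both readings are shown.

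**Trichomonas alone.** 2005 value = s × TMA value. With s = 0.5 it halves in 2005 and doubles back in 2006. For s = 0.4 to 0.6 the fall is 60% to 40%.

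**Composite** = 1 − Π(1 − p).

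*General population, s = 0.5.* Men, who carry no trichomonas component: 1 − 0.96 × 0.997 × 0.99 = 5.25%.
- If 5.2% is TMA: women 1 − 0.932 × 0.992 × 0.948 × 0.99 = 13.23%. With trichomonas at 2.6%, 10.85%. Pooled: 9.24% to 8.05%, a fall of 13% (then a rise of 15%).
- If 5.2% is culture, TMA is 10.4%: women 17.99%, and 13.23% by culture. Pooled: 11.62% to 9.24%, a fall of 20.5% (then a rise of 26%).
- Scaling gonorrhoea by the APTIMA confirmation shares in the gonorrhoea footnote (12% for self-collected swabs, 70% for urine) gives 11.28% to 8.89% on the culture reading, a fall of 21%.

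With syphilis at zero and gonorrhoea unscaled, the falls are 14% (TMA reading) and 22% (culture reading).

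For s = 0.6 on the TMA reading the pooled composite goes from 9.24% to 8.29% (a fall of 10%). For s = 0.4 on the culture reading (TMA 13.0%) it goes from 12.81% to 9.24% (a fall of 28%).

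*FSW, s = 0.5.*
- If 7.9% is TMA, syphilis 3.9%: 1 − 0.855 × 0.965 × 0.921 × 0.961 = 27.0%. With trichomonas at 3.95%, 23.8%, a fall of 12%.
- If 7.9% is culture (TMA 15.8%), syphilis zero: 30.5% to 24.0%, a fall of 21%.

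**Could false positives cancel the dip?** Suppose unconfirmed positives count in the three uncorrelated cities, cities are of equal size, and all have the same TMA prevalence p. With culture prevalence q in those three, the pooled dip vanishes when 17·s·p + 3q = 20p, that is q/p = (20 − 17s)/3. For s = 0.5 this is 3.8 (4.4 to 3.3 for s = 0.4 to 0.6): culture prevalence near 20% if p = 5.2%, or 40% if p = 10.4%. If only TMA-confirmed positives count, false positives drop out.

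**The case against.** The strongest reply is that nothing inferential depends on 2005. The primary model takes 2006 differences adjusted for 2002, the secondary endpoints use the same model, and the subgroup model uses 2006 data with a baseline covariate. This stands, and it confines the fault to description.

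A reader might infer that the composite must dip in 2005 and rebound in 2006. The documents do not support that. Section III does not say that the four-infection composite is shown for 2005. No section states the final 2005 classification rule. The documents also report unusually high culture prevalences in some cities, so the net pooled direction is uncertain.

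A reader might also set the artefact beside the 30-50% reduction used for power. That target is a contrast between arms, and an assay shift common to both arms does not mimic it. The Data Analysis Plan does list one graph of FSW infection rates over time in intervention cities only, where no control arm would cancel a shift. Its source is not stated and may be the mobile-team cycles.

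The DSMB had already questioned the culture data in April 2006 and asked for analyses without trichomonas. That covers the interim review, but section III was written later and still includes the 2005 value.

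Extending the point to chlamydia is tempting, since "Results from the 2002-03 and 2005 surveys are considered positive if initially AMPLICOR positive" while 2006 begins with APTIMA. The footnote there reports quite similar accuracy for the two assays, and no size can be given. Nor are 2002-03 and 2006 trichomonas identical: Appendix A requires TMA "performed on the specimen collected in the Gen-Probe collection media", and the survey footnote says "During the 2006 survey, an extra polyester swab was collected prior to the other 3 swabs". The documents do not show that this shifts prevalence materially.

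**Conclusion.** The point holds for descriptive trends only. The 2005 trichomonas value, and any four-infection composite that uses it, is not comparable with 2002-03 and 2006. With constant true prevalence, 50% sensitivity and no false positives, trichomonas reads about half. The pooled general-population composite reads about 13-21% low (syphilis 1%) and the FSW composite about 12-21% low. The lower ends apply if the baseline figures are already NAAT values. Observed values would also carry any real change and any false positives. If baseline were in fact culture, as the variables table says, the artefact would be a jump in 2006 and not a dip in 2005; the series would still not be comparable. No test, estimate or conclusion of the primary or secondary analyses is affected. This is a cheap improvement.

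**What to change.** In section III, estimate 2005 trichomonas on the TMA scale by city:

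share culture-positive × TMA-positive share among culture positives, plus share culture-negative × TMA-positive share among the tested culture negatives.

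This is valid only if the tested negatives were a random subset, which should be stated. As a check, suppose 5.2% are culture-positive, all confirmed, and 5.5% of culture negatives are TMA-positive: 0.052 + 0.948 × 0.055 = 0.104, which is twice the culture value, as 50% sensitivity implies.

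If the subset was not random, omit 2005 from the trichomonas and four-infection plots and show the three-infection composite, already defined as **CtGcSy**, for that year. In either case label the assay for each survey. Reconcile the **Tvresul** entry in the variables table (culture at baseline) with the laboratory section (TMA on all baseline swabs).

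The cost is a few lines of text and a small reweighting, with no new testing. The downside is a wider interval for 2005, or one point fewer on two plots.
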